8. SELECTION AND WITHDRAWAL OF PATIENTS

8.1. Patient Inclusion Criteria

To be eligible to participate in this trial, candidates must meet the following inclusion criteria:

1. Male or female patients aged 18 to 75 years, inclusive
2. Diagnosis of Crohn's disease for at least 2 months (prior to Screening) by clinical endoscopic evidence and corroborated by a histology report (Note: histopathology may be performed during Screening if no prior report is readily available).
3. Crohn's disease Activity Index score of 220 to 450 inclusive with an SES-CD score of ≥ 6 . (If disease isolated to ileum, the requirement will be a SES-CD score ≥ 4 .)
4. Average daily stool score ≥ 4 points and/or an average daily abdominal pain score of ≥ 2 points.
5. Patients must meet one of the following criteria:
 - Have an inadequate response or loss of response to at least one of the following Crohn's disease treatments :
 - Aminosalicylates, oral aminosalicylates ≥ 2.4 g/day or ≥ 3 g/day sulfasalazine for at least 4 weeks
 - Corticosteroids, oral prednisone ≥ 30 mg or budesonide ≥ 9 mg for at least 2 weeks or an equivalent (to oral prednisone) of intravenous corticosteroid for 1 week
 - Immunomodulators, oral azathioprine ≥ 1.5 mg/kg or 6-mercaptopurine 0.75 mg/kg (documentation of therapeutic level of 6-thioguanine is also acceptable) or methotrexate ≥ 12.5 mg/week for at least 8 weeks
 - Biologic therapy (TNF α antagonist or vedolizumab only) at an approved labeled dose used for induction therapy for at least 4 weeks or recurrence of disease activity despite scheduled maintenance therapy. (Biologic therapy exposed patients will be capped at 50% of total enrolled patients)
 - And/or have been intolerant to any of the above mentioned therapies (e.g., unable to achieve doses, dose levels, or treatment durations because of treatment related side effects and/or laboratory abnormalities)
6. The following background therapies for Crohn's disease will be permitted on a stable dose:
 - Oral aminosalicylates (e.g., mesalamine, sulfasalazine, olsalazine, balsalazide) at a stable dose for at least 3 weeks prior to Screening endoscopy
 - Prednisone (doses ≤ 20 mg per day) or equivalent at a stable dose (dose ≤ 9 mg per day) for at least 2 weeks prior to Screening endoscopy
 - Budesonide therapy at a stable dose for at least 2 weeks prior to Screening endoscopy

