4.2.1. Definitions

Table 2. Key Terms

Term	Definition
SES-CD	The sum of the scores for the 5 segments composed of the sum of 4 separate components that include: Size of ulcers, Extent of ulcerated surface, Extent of affected surface and the presence and type of narrowing. The 4 components are evaluated for each of the accessible segments and are scored as 0 to 3. The segments include: rectum, sigmoid & left colon, transverse colon, right colon and the ileum. The range of SES-CD scores is 0 – 12 for each segment, and 0 – 56 for the overall SES-CD score, with larger scores indicating greater severity of disease.
CDAI	The weighted sum of the 8 components: Number of liquid or soft stools for 7 days, Abdominal pain for 7 days, general well-being for 7 days, presence of complications, taking diarrhea medication, abdominal mass, hematocrit and percentage deviation from standard weight. The typical range of CDAI score is 0 to > 600 .
PRO2	The weighted sum of two items that separately contribute to the derivation of two CDAI sub-scores: $PRO2 = SF*7*2 + AP*7*5$. See Table 10, Appendix 3 for details.
SF/AP	The unweighted sum of two items that separately contribute to the derivation of two CDAI sub-scores: $SF/AP = SF + AP$. See Table 10, Appendix 3 for details. NOTE: This definition is included for reference only; in some clinical trials for Crohn’s disease, this has been used for various endpoints.
SF&AP	SF & AP Remission, defined as Average daily stool score ≤ 3 points AND average daily abdominal pain score ≤ 1 point
GHAS	Geboes Histology Activity Score
RHI	Robarts Histopathology Index

Table 3. Key Endpoints

Category or Shorthand	Label	Definition
Endoscopy	Endoscopic Change	SES-CD change from baseline
	Endoscopic Response-25	SES-CD decrease from baseline of $\geq 25\%$
	Endoscopic Response-50	SES-CD decrease from baseline of $\geq 50\%$
	Endoscopic Remission	SES-CD ≤ 4 points and a SES-CD decrease from baseline ≥ 2 points with no SES-CD sub-score > 1 point
CDAI	CDAI Change	CDAI change from baseline
	SF Change	SF Change from baseline
	AP Change	SF Change from baseline
	CDAI Clinical Response	CDAI decrease from baseline of ≥ 100 points
	CDAI Clinical Remission	CDAI score of <150
PRO2	PRO2 Clinical Response	PRO2 CD decrease $\geq 50\%$
SF&AP	SF & AP Remission	Average daily stool score ≤ 3 points AND average daily abdominal pain score ≤ 1 point
Histology	GHAS Change	GHAS change from baseline

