	GHAS Remission	No active inflammation in any measured segment; see Appendix 4 for details
	RHI Change	RHI change from baseline
	RHI Response - by Segment	RHI segment score decrease $\geq 50\%$
	RHI Remission- by Segment	No active inflammation in a measured segment
	RHI Remission	No active inflammation in any measured segment; see Appendix 4 for details
	Global RHI Score	A weighted sum of the worst of each of the four disease components across the four colonic segments; see Appendix 4 for details
Mucosal Healing	RHI Mucosal Healing	Endoscopic Remission combined with RHI Remission
Biomarkers	CRP Change	C-reactive protein change from baseline
	CRP Response-10	C-reactive protein < 10 mg/L
	FCP Change	Fecal calprotectin change from baseline
	FCP Response-250	Fecal calprotectin < 250 mcg/g

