5. GENERAL STATISTICAL CONSIDERATIONS

All efficacy and safety data will be listed by patient. Listings will be sorted by patient number and visit/study day.

Continuous data will be summarized using descriptive statistics: number of patients (n), mean, standard deviation (SD), standard error (SE), median, minimum and maximum.

Categorical data will be summarized using the number and percent of patients. When count or frequency data are presented, the percent will be suppressed when the count is zero in order to draw attention to the non-zero counts. A row denoted “Missing” will be included in count tabulations where necessary to account for dropouts and missing values. The denominator for percentages will be the number of patients within the population of interest, unless otherwise stated. Denominator for percentages in demographic and baseline categories will use the number of non-missing values. Non-zero percentages will be rounded to one decimal place, except 100% will be displayed without any decimal places.

Additional rounding rules are as follows:

- If the original value has 0 decimal places: mean, median, and CIs will have one decimal place and SD will have 2 decimal places;
- If the original value has 1 decimal place: mean, median, and CIs will have 2 decimal places and SD will have 3 decimal places; and
- If the original value has 2 or more decimal places: mean, median, CIs, and SD will all have 3 decimal places.

Minimum and maximum will always have the same decimal places as the original measure, up to a maximum of 3 decimal places.

Unless otherwise indicated, values that are collected with “<” sign and a numerical bound will be analyzed as half the numerical bound, without the sign in tables and figures. Values that are collected with “>” sign and a numerical bound will be analyzed as the numerical bound, without the sign. In listings, these data will be reported as collected, with the sign.

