7.2.2. Crohn's Disease History

The following CD history parameters will be summarized for the ITT population using descriptive statistics:

- Age at CD symptom onset (yr)
- Age at CD diagnosis (yr)
- Years since CD symptom onset
- Years since CD diagnosis
- Years since CD diagnosis category (0 - <2, 2 - <5, 5 - <10, 10 - <15, and ≥15)
- CDAI score at baseline
- CDAI score at baseline category (<330 and ≥330)

- Baseline Stool Frequency (daily average)
- Baseline Abdominal Pain (daily average)
- Category of days available for stool frequency and abdominal pain calculations (< 3, 3-6, >=7)
- SES-CD at baseline
- SES-CD at baseline category (< 12 and ≥ 12; ≥ median, < median)
- Baseline PRO2
- Baseline SF&AP
- Prior Corticosteroid use (Y/N)
- Prior Immunomodulator use (Y/N)
- Prior Biologics use (Y/N)
- Prior 5-ASA use (Y/N)
- Prior CD surgery History (Y/N)
- Baseline Fecal Calprotectin (microgram/g)
- Baseline Fecal Calprotectin (microgram/g) category (<250 and ≥250)
- Baseline CRP (mg/L)
- Baseline CRP (mg/L) category (<10 and ≥ 10)
- Baseline Enterocutaneous and/or Perianal Fistulas (Y/N)
- Draining Fistulas (Y/N)
- Non-Draining Fistulas (Y/N)
- Closed Fistulas (Y/N)
- Biological Response (Biologic Primary Non-responder vs All Others)
- Disease Location (Ileum only; Colon only; Ileocolonic (Ileum and Colon))
- Prior CD Surgery (Y/N)

Incomplete diagnosis dates will be imputed as detailed [Appendix 1](#).

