APPENDIX 5. DOCUMENT REVISION HISTORY

Version	Date	Notes/Revisions
1.0	March 03 2016	Initial version.
1.1	November 23 2016	Updated with details and additional analyses.
1.2	January 26 2017	Updated with details on missing data and other details.
1.3	June 1, 2018	
Updated to reflect the Week 12 and Week 52 summary tables generated for topline analyses, definition of treatment failure, as well as to reflect endpoint alterations and additional details regarding CDAI, SES-CD, GHAS, and RHI algorithms. Analysis of compliance rate categories has been excluded.
 
Following endpoints have been removed from the SAP
 
 • PRO CD SF+AP response-25 • PRO CD SF+AP response-50 • PRO CD SF+AP response-30 + 2P • PRO2 CD response-25 • SF&AP clinical response-2 • SF&AP clinical response-1 • Endoscopic remission-2 • Histologic improvement • Histologic response 
Following endpoints have been added to the SAP
 
 • CRP-response-10 • FCP response-250 • Fistula Response • GHAS Improvement • GHAS Remission • RHI Improvement • RHI Response • RHI Remission • Global RHI Score • RHI Mucosal Healing
1.4	August 28, 2019	
LOCF removed.
 
Treatment Failure rule is used in NRI
 
Efficacy graphs added

1.5	January 06, 2020	
Changes from data review meeting
 
 • PFT abnormality has been revised • Missing segment imputation of SES-CD has been added

		
• Lower bound of 0 for Hematocrit sub-score of CDAI has been added• Treatment failure criteria has been revised• RHI response analysis on all patients has been removed• RHI remission by segment for subset of segment score > 3 is replaced by RHI remission by segment for non-RHI remitters• CRP Change among patients having CRP \geq 10 mg/L at Baseline has been added• Analysis window has been added to Safety follow-up visits• Unscheduled and early termination visits are included in all analysis windows• Patients requiring cardiac monitoring is determined programmatically• Listing of non-trial procedures added• Section on PK analysis is removed and combined with Section on PD• Description of SDTM data in Section 5 is removed
--	--	---

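### As SAP Table 3 reads, CRP Response-10 and FCP Response-250 credit patients who start and stay below the cut-off; confirm the denominator and, if it is all patients, restrict it to those elevated at baseline

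*SAP*

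**What the plan says.** SAP 4.2.1, Table 3, gives the two biomarker responses as "C-reactive protein < 10 mg/L" and "Fecal calprotectin < 250 mcg/g". Neither row mentions the baseline value or a change. Every other Table 3 endpoint labelled as a response requires a fall. The two Endoscopic Response rows, for instance, begin "SES-CD decrease from baseline of" and then give 25% or 50%; CDAI, PRO2 and segmental RHI response are built the same way.

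Protocol 8.1 selects on clinical and endoscopic activity ("Activity Index score of 220 to 450 inclusive with an SES-CD score of" at least 6, or 4 for isolated ileal disease). Neither 8.1 nor 8.2 sets a minimum for CRP or calprotectin. SAP 7.2.2 tabulates "Baseline CRP (mg/L) category (<10 and ≥ 10") and "Baseline Fecal Calprotectin (microgram/g) category (<250 and ≥250"), the same cut-offs as the responses.

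On the denominator, SAP 5 states: "The denominator for percentages will be the number of patients within the population of interest, unless otherwise stated". SAP 5.4 makes that population all dosed patients. SAP 5.5.4 and 9.4 make NRI the primary method for proportions, with observed cases as sensitivity analysis. SAP 9.4 adds Clopper-Pearson intervals at Weeks 12 and 52.

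**The concern.** A response is normally read as a change brought about during treatment. Under the visible rule it can also be a normal value that was there before the first dose. Other absolute cut-offs in Table 3 are protected against this. CDAI remission is below 150, while entry requires 220 to 450. Stool-and-pain remission cannot be met by a patient who satisfies inclusion criterion 4. Endoscopic remission also requires a fall of at least 2 points. The two biomarker responses have no such protection, and the baseline split in SAP 7.2.2 shows that patients on both sides of the cut-offs are expected.

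Change in biomarkers is in the trial title and is an Induction secondary objective. With one arm there is no control rate to subtract, so a response rate that includes patients already below the cut-off can look like activity. It also mixes two quantities: how many patients started low, and how many came down.

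**Working it through.** **The plan's own figures.** SAP 5.1 gives 95% half-widths only for generic rates of 15% and 30%. They reproduce as 1.96 × √(p(1−p)/n): at n = 60, 9.0% for p = 0.15 and 11.6% for p = 0.30; at n = 30, 12.8% and 16.4%. No figure is given for CRP or calprotectin response.

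**Inputs.** N = 60 (SAP 5.1). The share below the cut-off at baseline, p0, is not in the documents and is assumed at 20%, 40% and 60%. The share missing or treatment failure, m, is assumed at 10% and 20% and independent of the baseline value.

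**Step 1: no patient changes.** Observed-case rate = p0. NRI rate = p0 × (1 − m); for example, 0.40 × 0.90 = 36% and 0.40 × 0.80 = 32%.

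| p0 | Observed, all patients (95% Clopper-Pearson) | NRI, m = 10% | NRI, m = 20% | Restricted to elevated at baseline (upper 95% limit) |
|---|---|---|---|---|
| 20% | 12/60 = 20% (10.8–32.3%) | 18% | 16% | 0/48 (7.4%) |
| 40% | 24/60 = 40% (27.6–53.5%) | 36% | 32% | 0/36 (9.7%) |
| 60% | 36/60 = 60% (46.5–72.4%) | 54% | 48% | 0/24 (14.2%) |

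**Step 2: values vary within patients, with no systematic shift.** Take log values as bivariate normal with correlation ρ (assumed), c = Φ⁻¹(p0), and B = the probability of being below c at both times. Then P(stay below) = B/p0 and P(cross from above) = (p0 − B)/(1 − p0).

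| p0 | ρ = 0.9: stay / cross | ρ = 0.7: stay / cross |
|---|---|---|
| 20% | 75.0% / 6.3% | 56.5% / 10.9% |
| 40% | 82.6% / 11.6% | 69.4% / 20.4% |
| 60% | 88.4% / 17.4% | 79.6% / 30.6% |

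The all-patient rate stays at p0: for p0 = 40% and ρ = 0.7, 0.40 × 0.694 + 0.60 × 0.204 = 0.40. The crossing column is the no-effect rate in the restricted set. At ρ = 0.7 it is about half the all-patient rate (20.4% against 40%); at ρ = 0.9 it is under a third (11.6% against 40%).

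**Step 3: drift without drug effect.** Patients enter on active disease, so values may fall anyway. A downward shift of 0.2 SD moves the all-patient rate from 40% to Φ(Φ⁻¹(0.40) + 0.2) = 47.9%.

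**Step 4: interpretability.** If a share q of elevated patients comes below the cut-off and the others stay put, the all-patient observed rate is p0 + (1 − p0)q. With p0 = 40% and q = 30% it is 0.40 + 0.60 × 0.30 = 58%. With p0 = 60% and q = 0 it is 60%. The inactive case gives the higher figure.

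**The case against.** The strongest objection is that the denominator cannot be seen. This SAP places baseline restrictions outside Table 3: the segmental RHI response row has none there, but the list in 4.2.2 limits it to patients not in RHI remission at baseline. The lines of 4.2.2 where the biomarker endpoints would stand are redacted, the body of Table 6 is not readable, and Section 9.5, which SAP 12 cites, is not in the available text. Appendix 5 records for version 1.5 that "CRP Change among patients having CRP \geq 10 mg/L at Baseline has been added", yet this analysis appears nowhere in the visible body. A restricted biomarker analysis can therefore exist out of sight. This objection stands and makes the point conditional. It does not make the visible definition sound, and that log entry concerns CRP Change, not either response.

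The harm is also limited. CRP Change and FCP Change are summarised by visit, CRP has laboratory shift tables, and the baseline categories in SAP 7.2.2 let a reader see p0. A reader might infer that the trial cannot show whether either marker fell; these analyses contradict that. They do not correct a rate labelled as a response, because p0 sits in a different table.

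Finally, the restriction selects on a high baseline and so brings in regression to the mean. That stands too: at ρ = 0.7 about 11% to 31% of elevated patients cross by chance. It would be wrong to say that the restriction generally removes most of the no-effect rate.

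**Conclusion.** The point holds conditionally and with limited impact. On the visible text, both responses credit patients who start and stay below the cut-off. With no change in any patient, the rate is p0 for observed cases and p0 × (1 − m) under the primary NRI; at p0 = 40% that is 40%, or 36% and 32% at m = 10% and 20%. The size rests on assumed p0, m and ρ, since the documents give none of them.

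Two stronger readings are not supported. One is that the SAP certainly applies no baseline restriction: the relevant text is redacted or unreadable, so this can be neither confirmed nor ruled out. The other is that the no-effect rate simply equals the baseline share: NRI lowers it and downward drift raises it. Both endpoints are descriptive and non-primary, and SAP 5.3 plans no hypothesis tests, so neither the primary endpoint nor any formal conclusion is affected.

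**What to change.** First, the sponsor should confirm whether the endpoint lines in SAP 4.2.2, Table 6 or Section 9.5 already limit these responses to patients elevated at baseline. If they do, a cross-reference in Table 3 is enough.

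If they do not:

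- Report CRP Response-10 among patients with baseline CRP of at least 10 mg/L, and FCP Response-250 among those with baseline calprotectin of at least 250 mcg/g, with NRI and Clopper-Pearson intervals in those subsets. Baseline should be as defined in SAP 5.5.1, and the number of patients without a baseline value should be stated.
- Keep the all-patient figure under the label 'proportion below cut-off', beside the same proportion at baseline.
- Note under the table that some elevated patients will cross without a drug effect.

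The cost is SAP wording and one filter on categories already derived for SAP 7.2.2; no new data are needed. The price is a smaller denominator (36 of 60 at p0 = 40%), a wider interval and some remaining regression to the mean.

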4.2.2. Efficacy Endpoints for Induction Period

Primary Efficacy Endpoint

- Endoscopic Change

Other Efficacy Endpoints

- Category: Endoscopy

- Proportion of patients with Endoscopic Response-25
- Proportion of patients with Endoscopic Response-50
- Proportion of patients with Endoscopic Remission
- Category: CDAI
 - CDAI Change
 - SF Change
 - AP Change
 - Proportion of patients with CDAI Clinical Response
 - Proportion of patients with CDAI Clinical Remission
- Category: PRO2
 - Proportion of patients with PRO2 Clinical Response
- Category: SF&AP
 - Proportion of patients with SF&AP Remission
- Category: Histology
 - GHAS Change
 - Proportion of patients with GHAS Remission
 - RHI Change
 - Global RHI Score Change
 - Proportion of patients with RHI Response - by segment among non-RHI remitters at Baseline
 - Proportion of patients with RHI Remission
 - Proportion of patients with RHI Remission - by segment
 - Proportion of patients with RHI Remission - by segment among non-RHI remitters at Baseline
- Category: Mucosal Healing
 - Proportion of patients with RHI Mucosal Healing
- [REDACTED]
- [REDACTED]
- [REDACTED]
- [REDACTED]
- [REDACTED]
- [REDACTED]

– [REDACTED]

4.2.3. Efficacy Endpoints for Extension Period

The efficacy endpoints for the induction period listed above in section 4.2.2 will be evaluated for all extension visits.

In addition, proportion of patients achieving remission and remaining corticosteroid-free in the prior 12 weeks will be evaluated at each time point of Week 36, Week 48, and Week 52, among the patients who received corticosteroids for CD at baseline. This analysis will be performed for CDAI Remission and SF&AP Remission.

Clinical Remission (Based on CDAI) at both Week 12 and Week 52 will also be summarized. Following efficacy graphs will be presented.

- CDAI change from Baseline (Observed) showing mean and 95% CI at each scheduled visit up to Week 52, overall and by Biologic Exposed vs. Biologic Naïve
- CDAI (Observed) showing mean and 95% CI at each scheduled visit up to Week 160, overall and by Biologic Exposed vs. Biologic Naïve
- Bar graph of CDAI Clinical Response (NRI) at Week 12 and Week 52, overall and by Biologic Exposed vs. Biologic Naïve
- Bar graph of CDAI Clinical Response (Observed) at Week 12 and Week 52, overall and by Biologic Exposed vs. Biologic Naïve
- Bar graph of CDAI Clinical Remission (NRI) at Week 12 and Week 52, overall and by Biologic Exposed vs. Biologic Naïve
- Bar graph of CDAI Clinical Remission (Observed) at Week 12 and Week 52, overall and by Biologic Exposed vs. Biologic Naïve
- Bar graph of Endoscopic Response-50 (Paired Segments, NRI) at Week 12 and Week 52, overall and by Biologic Exposed vs. Biologic Naïve
- Bar graph of Endoscopic Response-50 (Paired Segments, Observed) at Week 12 and Week 52, overall and by Biologic Exposed vs. Biologic Naïve
- Stool frequency change from Baseline (Observed) showing mean and 95% CI at each scheduled visit up to Week 52, overall and by Biologic Exposed vs. Biologic Naïve
- Stool frequency (Observed) showing mean and 95% CI at each scheduled visit up to Week 160, overall and by Biologic Exposed vs. Biologic Naïve

- Abdominal Pain change from Baseline (Observed) showing mean and 95% CI at each scheduled visit up to Week 52, overall and by Biologic Exposed vs. Biologic Naïve
- Abdominal Pain (Observed) showing mean and 95% CI at each scheduled visit up to Week 160, overall and by Biologic Exposed vs. Biologic Naïve

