6.1.4. Extension Period Secondary Objectives

- To characterize endoscopic improvement at Week 52
- To characterize the histopathological changes of the intestinal mucosa at Week 52
- To characterize the effect of RPC1063 in maintaining clinical improvement over time

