7.1.2. Extension Period

All patients will receive RPC1063 1 mg daily dose in the Extension Period and may receive treatment through Week 160. During the Extension Period, the investigator should continue to assess the patients clinical status and based on clinical judgment determine if the patient should continue or withdraw from the trial and receive alternative therapy. Extension Period visit schedule and procedures, including early termination and safety follow-up, are provided in [Table 3](#).

Patients who complete the Week 160 visit may have the option to immediately enter (without completing the 30-day or 90-day Safety Follow-up Visits) the open-label extension Phase 3 CD Study [REDACTED].

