13.2. Statistical Methods

13.2.1. General Considerations

All efficacy and safety data will be listed by patient and summarized. Baseline is defined as the last observed measurement prior to the Induction Period Day 1 receipt of investigational drug.

In general, descriptive summaries will be presented for the efficacy and safety variables collected. Continuous variables will be summarized using number of patients (n), mean, standard deviation (SD), median, minimum, and maximum. Categorical variables will be summarized using frequency counts and percentages.

There will be no imputation for missing efficacy or safety observations

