5.5.4. Handling of Missing and Partial Data

For all proportion-based efficacy endpoints, patients with missing efficacy data and the responses after treatment failure will be considered non-responders (NRI) in the primary analyses.

Treatment failures at Week 12 and Week 52 will be determined based on the rules listed in Section 9.1. In all analyses where NRI is used, responses of the patients who are treatment failures at Week 12 will be imputed as non-responder at Week 12 and onwards. In addition, responses of the patients who are treatment failures at Week 52 will be imputed as non-responder at Week 52 and onwards.

Continuous efficacy endpoints will not be imputed.

Sensitivity analyses on missing data on selected endpoints are detailed in the efficacy analyses sections 9.1 and 9.2.

With the exception of partial dates, missing demographic, disposition, baseline characteristics, medical history, and safety data will be analyzed using observed data only, without imputation. For

partial dates, the algorithms for imputation will vary depending upon the parameter; the details can be found in [Appendix 1](#).

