9.3. Continuous Efficacy Endpoints

For continuous efficacy endpoints, the number of patients (n), mean, standard deviation (SD), standard error (SE), median, minimum and maximum will be presented for the actual values and change from baseline at all scheduled visits. It is noted that percent change from baseline may be displayed for certain endpoint variations, based on the TFL shell specifications. 95% CI presented in efficacy graphs will be computed using the t distribution.

All continuous efficacy endpoints will be tabulated by scheduled visit. This includes (see [Table 3](#)) Endoscopic Change, CDAI Change, GHAS Change, RHI Change, CRP Change, and FCP Change. Per Section 5.5.3, efficacy data will be associated with Visits according to analytic visit windows.

In all cases, the primary analysis will be based on observed cases.

The list of continuous efficacy endpoints is shown in [Table 5](#) below:

Table 5. Continuous Endpoints and Imputation Methods

Continuous Efficacy Endpoints	Method(s)
Endoscopic Change (Paired Segments, Total Score)	OC
CDAI Change	OC
SF Change	OC
AP Change	OC
GHAS Change from Baseline (Paired Segments, Total Score)	OC
RHI Change from Baseline (Paired Segments, Total Score)	OC
C-RP Change from Baseline	OC
FCP Change from Baseline	OC
Global RHI Score	OC

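### The Extension curves of CDAI, stool frequency and abdominal pain average whoever is observed at each visit, so withdrawal on clinical status can make them improve with no within-patient change

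*SAP*

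**What the plan says.** SAP 4.2.3 lists six line graphs. CDAI has one of change, "CDAI change from Baseline (Observed) showing mean and 95% CI at each scheduled visit up to Week 52", and one of the score itself, "CDAI (Observed) showing mean and 95% CI at each scheduled visit up to Week 160, overall and by Biologic Exposed vs. Biologic Naïve". Stool frequency and abdominal pain each have the same pair.

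SAP 9.3 says of continuous endpoints: "In all cases, the primary analysis will be based on observed cases". Its Table 5 lists observed cases as the only method for CDAI, SF and AP Change, and the graph intervals are t intervals. SAP 5.5.4 adds "Continuous efficacy endpoints will not be imputed", and Protocol 13.2.1 has "There will be no imputation for missing efficacy or safety observations". The treatment-failure rules in SAP 9.1 work through NRI, so they do not touch these means. The version 1.5 entry in SAP Appendix 5 places early-termination visits in the analysis windows, so a leaver's last value counts once.

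On who stays, Protocol 7.1.2 has the investigator "assess the patients clinical status and based on clinical judgment determine if the patient should continue or withdraw from the trial and receive alternative therapy". Protocol 7.1.1 asks for the same judgment at the end of Induction. Protocol 8.3 lists lack of efficacy among the reasons for discontinuation and does not replace leavers. One Extension secondary objective (Protocol 6.1.4) is "To characterize the effect of RPC1063 in maintaining clinical improvement over time".

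**The concern.** The patients behind each plotted point change from visit to visit, and the rule for leaving refers to the condition that the graphs measure. If patients with high scores leave more often, the mean of those remaining improves through selection alone. The change graphs at least compare each patient with their own baseline. The raw-score graphs to Week 160 do not: an early point covers nearly everyone dosed and a late point only those who stayed. The biologic-exposed and biologic-naive curves could also separate merely because the two groups leave at different rates.

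What is at stake is how the curves are read. Each would carry a 95% CI that reflects only sampling error among those present, and could be taken as evidence of maintained or growing benefit. SAP 11.1 foresees results going to congresses, journals and regulatory filings.

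**Working it through.** **Inputs.** From the documents: about 60 patients, and a 30% response rate (Protocol 13.1, SAP 5.1). The plan's precision figure for that rate reproduces: 1.96 × √(0.30 × 0.70 / 60) = 11.6 points. It does not concern these curves, and the plan does not say that the 30% is CDAI response. Everything else is assumed: SD of CDAI change 70–90, within-patient correlation 0.5–0.7, and the withdrawal pattern.

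**1. Selection alone.** Hold every patient constant, 30 at CDAI 100 and 30 at 300.
- All present: (30 × 100 + 30 × 300) / 60 = 200.
- Ten high scorers leave: (3,000 + 6,000) / 50 = 180.
- Twenty leave: (3,000 + 3,000) / 40 = 150.

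Observed remission (CDAI below 150) goes from 30/60 = 50% to 30/50 = 60% and 30/40 = 75%. Under NRI it stays at 50%.

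**2. One round of withdrawal after Week 12.** Let the true mean change be the same at every visit and set it so that 30% reach −100. With SD 90 it is −100 + 0.524 × 90 = −52.8; with SD 70 it is −100 + 0.524 × 70 = −63.3. Non-responders lie on average φ(0.524)/0.70 = 0.348/0.70 = 0.497 SD above the mean. If a fraction q of them (70% of patients) leaves, the mean at later visits shifts by

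ρ × SD × 0.497 × 0.70q / (1 − 0.70q).

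- Mild (q = 0.25), SD 70, ρ 0.5: 0.5 × 70 × 0.497 × 0.175/0.825 = 3.7 points; 3.7/63.3 = 6%.
- Mild, SD 90, ρ 0.7: 0.7 × 90 × 0.497 × 0.175/0.825 = 6.6 points; 6.6/52.8 = 13%.
- Strong (q = 0.50), SD 90, ρ 0.7: 0.7 × 90 × 0.497 × 0.35/0.65 = 16.9 points; 16.9/52.8 = 32%.

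**3. Continuing withdrawal (simulation, SD 90, ρ 0.7).** Mild means that 5% of everyone leaves at each later visit. Strong means that 15% of non-responders and 5% of responders leave.

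| Pattern | Observed at Week 52 | Observed mean at Week 52 | Excess over −52.8 |
|--|--|--|--|
| Mild | 71% | about −59.5 | 12–13% |
| Strong, early-termination value not counted | 46% | about −78 | 47–48% |
| Strong, each leaver's value counted in the next window | 46% still in trial | about −75 | 42% |

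In the mild pattern the excess stays at 12–13% at every later visit. In the strong pattern it keeps rising.

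**4. Early-termination values.** Protocol Table 2 lets a patient who does not continue return up to 4 weeks after Week 12. That can fall in the SAP Week 24 window (days 99–210). If all such values land there, the Week 24 excess vanishes and later drift is delayed by about one visit.

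**5. Raw scores to Week 160.** A second simulation used 60 patients with constant scores (assumed mean 200, SD 100) and counted the early-termination value in its own window. With withdrawal related to score, drift at Week 160 was −19 to −49 points at 59–66% retained, and −37 to −70 at 42–43% retained. With withdrawal unrelated to score it was between −0.4 and +0.9.

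**6. What a repeated-measures model does.** In the step 3 patterns at SD 90, a likelihood mean using all visits returned about −53. In a version of step 5 with within-patient noise (SD 40, 41% retained at Week 160), observed means drifted −27 at Week 52 and −58 at Week 160, against −1.0 and +0.7 for a random-intercept model. Withdrawal depended only on recorded scores here, so the model's assumption held by construction.

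**The case against.** The strongest reply is that the maintenance objective is already protected. The over-time clinical endpoints in Protocol 6.2.2 are proportions. SAP 5.5.4 and 9.4 make NRI primary for them, they are tabulated at every scheduled visit, and NRI bar graphs are planned for Weeks 12 and 52. In the strong pattern, NRI response falls from 30% at Week 12 to 19% at Week 52 and 9% at Week 160, so the plan's main maintenance result would show loss while the observed curve improved. This stands. A reader might infer that the objective rests on the curves; the documents do not support that.

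A reader might also infer that investigators are told to withdraw poor responders. Protocol 7.1.2 asks them to assess and decide, and gives no threshold. Selective leaving is likely, not prescribed.

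The drift can also be small beside sampling error. At Week 52 in the mild pattern about 0.71 × 60 = 43 patients remain, and the half-width is roughly 2.02 × 90/√43 = 28 points against an excess of about 7. That limits the practical weight of the mild case, but the interval is still centred in the wrong place.

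The graphs are labelled as observed, the tables give n, and SAP 6 tabulates discontinuations with reasons. This discloses attrition without removing the drift. The graph list does not ask for n, but the graph shells are not in the text, so its absence from the figures is unproven. SAP Table 6 and Section 9.5 are also not in the text available here, so a relevant analysis there cannot be excluded.

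**Conclusion.** The point holds as a limit on how the six Extension curves can be read. For the change graphs, the claim means apparent further improvement after Week 12 with no change in any patient after Week 12.

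The excess in mean CDAI change at Week 52 runs from about 6% (mild attrition, SD 70, correlation 0.5) to about 42–48% (strong attrition, SD 90, correlation 0.7). These are illustrations on assumed inputs, not estimates, and with withdrawal unrelated to score the drift is nil.

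Two stronger readings should be resisted. One is that the bias must grow to Week 160. It does so only if score-related withdrawal continues; in the mild pattern it is one step and then flat. The other is a near doubling at Week 160: the strong pattern does give −103 against −53 (+95%) there, but no planned graph shows change beyond Week 52, and only 17% of patients, about 10 of 60, would remain.

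The Week 12 SES-CD endpoint is not affected by this point. It is a cheap improvement to supportive displays in a descriptive trial.

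**What to change.** In SAP 9.3 and 4.2.3:
- Keep the observed means. Add, as a sensitivity curve for CDAI, SF and AP Change, a repeated-measures mixed model with visit as a factor, baseline as a covariate and all on-treatment visits of all dosed patients. Use a structured covariance if the unstructured one does not converge.
- State that the model assumes missing at random and estimates the course had patients stayed on drug.
- Print n under every visit on every graph.
- Add change from each patient's own baseline to the graphs that run to Week 160; SAP 9.3 already tabulates it at all scheduled visits.
- If a cohort display is wanted, restrict it to a fixed cohort such as Week 52 or Week 160 completers, labelled as such. A line for all patients who left is not a fixed cohort, because they leave at different visits.

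The model should not replace the observed means as the main curve, because Protocol 13.4 commits efficacy reporting to descriptive statistics. It can be recorded in SAP 12 as an added analysis. It imputes nothing, so it does not breach Protocol 13.2.1.

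The cost is SAP wording and one standard model on data already collected from Week 4. The downsides are the missing-at-random assumption, which the data cannot confirm, and wide intervals at late visits.
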